8. SAFETY ANALYSES

The safety analysis will be conducted on the Safety Analysis Set, defined in Section 3.1.3 unless otherwise noted.

8.1. Adverse Events and Deaths

Up to 3 different displays of adverse event data may be presented as described in Section 3.2 of this SAP:

“As-treated” analysis: Subjects who switched from placebo to open-label filgotinib will have adverse events occurring while on double-blind study drug summarized with placebo, and adverse events occurring on/after first dose date of open-label filgotinib to last dose date of filgotinib plus 30 days (if permanently discontinued), or all available data if ongoing at time of an interim analysis summarized with filgotinib. All other subjects will have adverse events occurring on/after first dose date of any study drug to last dose date of any drug plus 30 days (if permanently discontinued), or all available data if ongoing at time of interim analysis summarized by treatment received. This analysis will summarize all on-treatment adverse events and will be used to scan for all safety events during the study.

During Double-Blind Phase of the Study: Data will be included up to first dose date of open-label filgotinib minus 1 day for subjects who switched to open-label filgotinib; last dose date of double-blind study drug plus 30 days for those who have permanently discontinued from study drug; or all available data while on double-blind drug if ongoing at the time of an interim analysis. This analysis will summarize adverse events during the same timeframe as the primary analysis for sperm/semen data.

During Open-Label Filgotinib Phase of the Study: Data will be included from OL Day 1 to last dose date of open-label filgotinib plus 30 days for those who have permanently discontinued from open-label filgotinib; or all available data if ongoing at the time of an interim analysis. These displays will summarize data for subjects in the Open-Label Filgotinib Safety Analysis Set. This analysis appropriately adjusts the denominator for interruptions and discontinuations for open-label filgotinib to only those subjects who took open-label filgotinib.

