	Screening	Part A (Section 6.4)					Part B (Section 6.5)		Open-Label Filgotinib Phase (Section 6.6)					Long Term Extension (Section 6.10)	30 Day Safety Follow-up ^e	ET ^f	
		Day 1	Wk 2	Wk 4	Wk 8	Wk 13 ^a	Wk 20	Wk 26 ^a	Sperm Parameter Eligibility Confirmation ^b	OL Day 1	OL Wk 2	OL Wk 4	OL Wk 8	OL Wk 13 ^c			LTE Week 13 through LTE Week 195 ^d
		45 days	±5 days	±5 days	±5 days	+ 5 days	±5 days	+ 5 days			±5 days	±5 days	±5 days	+ 5 days			±10 days
Study Procedure																	
Semen Collection (2 samples as per collection instructions in Section 6.13) ^g	X ^e				X		X	X ^g					X ^e	X		X	
Date and time of most recent ejaculation ^g	X				X		X	X					X	X		X	
HIV, Hepatitis B, and Hepatitis C ^v	X																
HBV DNA ^w					X		X						X	X			
Randomization		X															
Study Drug Accountability				X	X	X	X	X		X		X	X	X	X	X	
Study Drug Dispensation		X		X	X	X	X	X		X		X	X	X	X		
PK collection (sparse)			X ^s	X ^t		X ^z		X ^z			X ^s	X ^t		X ^z			
In-Clinic Dosing ^{aa}		X	X			X		X			X			X			

a Weeks 13 and 26 must occur after 13 weeks and 26 weeks of drug exposure, respectively. Therefore, visit window for these visits are +5 days

b Subjects on blinded study drug meeting criteria as a non-responder (Week 13) or for Disease Worsening (after Week 13 through 26), and not meeting the pre-specified decrease threshold in sperm parameters, are eligible for open-label filgotinib (refer Appendix 11 and Section 3). For definitions of IBD response status, Disease Worsening, and/or pre-specified decrease threshold in sperm parameters please refer to Definition of Terms and Section 3.4.

c OL Week 13 must occur after 13 weeks of starting open-label filgotinib. Therefore, visit window is +5 days.

d Subjects in the LTE will undergo scheduled visits for safety assessments and semen sample collection every 13 weeks, starting with LTE Week 13. Semen monitoring will be collected until the Week 13 primary study results are analyzed.

e Any time a subject discontinues study drug, a safety follow-up visit, 30 days (± 5 days) after the last dose of study drug is required, even if the subject is entering the Monitoring Phase

f Any time a subject discontinues participation in the study prior to Week 26, OL Week 13, reaching reversibility or Monitoring Phase Week 52 (whichever occurs first), or LTE Week 195, an ET Visit is required. Subjects who are Responders at Week 26 or at OL Week 13 and choose not to continue in the LTE are also required to complete ET visit assessments.

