Subjects will visit the clinical study center at Screening, Day 1, Week 2, Week 4, Week 8, and Week 13 (Part A of study). Subjects who are IBD responders at Week 13 without meeting pre-specified sperm decrease thresholds will continue on blinded treatment and return for Week 20 and Week 26 assessments. A pre-specified sperm decrease threshold was defined as a $\geq 50\%$ decrease from baseline in sperm concentration prior to Protocol Amendment 2; and a $\geq 50\%$ decrease from baseline in sperm concentration and/or motility and/or morphology at/after Protocol Amendment 2. Since no subject demonstrated a $\geq 50\%$ decrease in sperm motility or morphology prior to Protocol Amendment 2, this SAP will hereafter refer to a “pre-specified sperm decrease threshold” as a subject demonstrating a $\geq 50\%$ decrease from baseline in sperm concentration and/or motility and/or morphology. Subjects who are non-responders at Week 13 and subjects who have disease worsening after Week 13 up to Week 26 who do not meet pre-specified sperm decrease thresholds will enter the Open-Label Phase and return for visits at Week 2, Week 4, Week 8, and Week 13 during the open-label phase. Subjects who are responders at Week 26/Open-label Week 13 without disease worsening and without meeting pre-specified sperm decrease thresholds may continue taking study drug in the LTE phase for up to 195 weeks (or until they have disease worsening or meet pre-specified sperm decrease threshold[s]).

Subjects who meet pre-specified sperm decrease threshold(s) at any postbaseline visit will stop study drug, switch to a standard of care regimen selected by the investigator (in accordance with the protocol) and enter the Monitoring Phase. Subjects will undergo semen evaluations every 13 weeks starting from their entry into the Monitoring Phase for up to 52 weeks or until reversibility is met, whichever is achieved first. Reversibility is defined as a return to $> 0.5 \times$ (mean of 2 evaluable samples collected at screening visit) of all sperm parameter(s) qualifying the subject for the monitoring phase—based on 2 evaluable samples collected at the monitoring phase visit.

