Adverse events will additionally be displayed for the double-blind treatment phase (to align with the period summarized for the primary analysis of semen data). Data will be summarized by double-blind treatment group (ie, filgotinib 200 mg or placebo) from first dose date of double-blind study drug up to the first dose date of open-label filgotinib (minus 1 day for AEs) for subjects who switch to open-label filgotinib; to last dose date of double-blind study drug + 30 days for subjects who stop double-blind study drug and do not switch to open-label filgotinib; or all available data at time of interim analysis (for subjects ongoing on double-blind treatment at the time of an interim analysis).

Select AE summaries (eg, brief summary of AEs while on open-label filgotinib, AEs leading to interruption of open-label filgotinib, and AEs leading to discontinuation of open-label filgotinib) will be displayed for subjects in the Open-Label Filgotinib Safety Analysis Set. AEs occurring from first to last dose date of open-label filgotinib plus 30 days (for those permanently discontinued from drug) or all events on/after open-label first dose date for those ongoing on open-label filgotinib will be included.

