Week 221	1548	1535	≥ 1548
FU-4*	Last Dose Date any study drug + 30 days	Last Dose Date any study drug + 8 days	Last Dose Date any study drug + 35 days

Note: Primary analysis includes data up to first dose date of open-label filgotinib (if non-missing) or to last dose date of double-blind drug + 7 days (for those who do not switch to open-label filgotinib).

Secondary analysis includes all “on-treatment” data up to the last dose date of any study drug + 7 days.

*FU-4 visit for subjects who have stopped all study drugs and had a 30-day safety FU visit ± 5 days will be displayed in listings only.

Table 3-4. Analysis Visit Windows for On-Treatment Semen Parameters

Analysis Visit	Nominal Day (Study Day)	Lower Limit (Study Day)	Upper Limit (Study Day)
Baseline	1	None	1
Week 13	92	85	112
Week 26	183	170	260
Week 39	274	261	351
Week 52	365	352	442
Week 65	456	443	533
Week 78	547	534	624
Week 91	638	625	715
Week 104	729	716	806
Week 117	820	807	897
Week 130	911	898	988
Week 143	1002	989	1079
Week 156	1093	1080	1170
Week 169	1184	1171	1261
Week 182	1275	1262	1352
Week 195	1366	1353	1443
Week 208	1457	1444	1534
Week 221	1548	1535	≥ 1548

Note: Primary analysis includes data up to first dose date of open-label filgotinib (if non-missing) or to last dose date of double-blind drug + 7 days (for those who do not switch to open-label filgotinib).

Secondary analysis includes all “on-treatment” data up to the last dose date of any study drug + 7 days.

Table 3-5. Analysis Visit Windows for Semen Parameters in Monitoring Phase (Calculated from Last Dose Date of Any Study Drug)

Analysis Visit	Nominal Day (FU Day)	Lower Limit (FU Day)	Upper Limit (FU Day)
MP Week 13	91	8	104
MP Week 26	182	105	195
MP Week 39	273	196	286
MP Week 52	364	287	377

MP = Monitoring Phase; FU = Follow-Up.

NOTE: All visit windows for monitoring phase will be calculated from last dose date of any study drug.

FU Day = visit date – last dose date of any study drug.

Investigator Assessment of ECG Visit Assignment

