6.2. Primary Analysis of Primary and Secondary Endpoints

The primary analysis will be an observed cases analysis at Week 13 while subjects are on double-blind study drug as described in FDA’s guidance for industry on testicular toxicity studies {U. S. Department of Health and Human Services (DHHS) 2018}.

The main estimators of a While on Treatment Strategy estimand will be utilized for the primary analysis of primary and secondary endpoints at Week 13:

BINARY ENDPOINT	WHILE ON-TREATMENT STRATEGY
Population	Semen Analysis Set (subjects with 2 evaluable semen samples collected at baseline and at the Week 13 analysis visit) as defined in Section 3.1.2 of this SAP.
Patient Level Outcome to be Measured	Binary outcome for a subject meeting a $\geq 50\%$ decrease from baseline in sperm concentration at Week 13. Outcome is determined based on the mean of 2 evaluable semen samples at a visit.
Measure of intervention effect and handling of intercurrent events	Measure of treatment effect assuming that the treatment effect prior to the intercurrent event of treatment early termination is of interest. Data included to last dose date double-blind drug + 7 days will be considered “while on-treatment” for those who permanently discontinue double-blind study drug.
Population level summary measure	Difference in a binary outcome, comparing those assigned to filgotinib versus those assigned to placebo.
Estimators	
Main estimator: A stratified Mantel-Haenszel test (stratification factor: sperm concentration [15 - 50 and > 50 M/mL]) will be used to estimate the difference in proportions (filgotinib – placebo) and corresponding 95% CI {Koch 1989}. Calculations are provided in Appendix 2.
 
Note: When performing the stratified Mantel-Haenszel test, the 15 - 25 and > 25 - 50 M/mL strata for sperm concentration will be combined (eg, 15 - 50 M/mL) due to the small number of subjects in the lowest stratum; disease type will not be included as a stratification factor due to the small number of subjects with CD; and no subjects in this study received MTX.

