8.1.6. Summaries of Adverse Events and Deaths

A brief, high-level summary of the number and percentage of subjects who experienced at least 1 TEAE in the categories described below will be provided by treatment for the double-blind phase, open-label filgotinib phase, and for an “as-treated” display:

- TEAE
- TEAEs with Grade 3 or higher (further broken down to Grade 3, Grade 4, and Grade 5)
- TEAEs with Grade 2 or higher
- TE treatment-related AE
- TE treatment-related AEs with Grade 3 or higher (further broken down to Grade 3, Grade 4, and Grade 5)
- TE treatment-related AEs with Grade 2 or higher
- TE SAE
- TE treatment-related SAE

- TEAE that led to premature discontinuation of double-blind study drug (displayed for double-blind phase analysis only)
- TEAE that led to premature discontinuation of open-label filgotinib study drug (displayed for open-label phase analysis only)
- TEAE that led to temporary interruption of double-blind study drug (displayed for double-blind phase analysis only)
- TEAE that led to temporary interruption of open-label study drug (displayed for open-label phase analysis only)
- TEAE that led to premature discontinuation of study
- All deaths observed in the study (if subject received ≥ 1 dose of open label filgotinib will be summarized with open-label filgotinib; if last study drug received was double-blind, will be summarized with double blind study drug)

The number and percentage of subjects who experienced at least 1 TEAE will be provided and summarized by SOC, HLT, PT, and treatment for the double-blind phase and for an “as-treated” analysis.

The following 2 tables will be displayed for the double-blind phase of the study for subjects in the Safety Analysis Set:

- The number and percentage of subjects who experienced TEAEs leading to temporary interruption of double-blind study drug
- AEs leading to premature discontinuation of double-blind study drug

Similar tables will be displayed for the open-label filgotinib phase of the study for subjects in the Open-Label Filgotinib Safety Analysis Set:

- The number and percentage of subjects who experienced TEAEs leading to temporary interruption of open-label filgotinib
- AEs leading to premature discontinuation of open-label filgotinib

For other AEs described below, summaries (for the double-blind phase and for “as-treated” analysis) will be provided by SOC, PT, and treatment:

- All TEAEs

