8.1.7. Adverse Events of Interest

Adverse events of interest (AEIs) include infections, gastrointestinal perforations, herpes zoster, malignancies (excluding non-melanoma skin cancers), non-melanoma skin cancers, and thromboembolic events. Summaries of the following treatment-emergent AEIs will be produced to enhance the analysis of safety data.

- Events of infection presented in the following subcategories:
 - AEs of infections, utilizing all AEs in the MedDRA Infections and Infestations SOC
 - AEs of serious infections, using all AEs in the MedDRA Infections and Infestations SOC that are classified as SAEs
 - AEs of herpes zoster, utilizing a MedDRA search term (MST) list developed by Gilead
 - AEs of opportunistic infections (OIs), using a Standardized MedDRA Query (SMQ)--narrow scope
 - Active tuberculosis, using an MST list developed by Gilead
 - Hepatitis B or C infections, using an MST list developed by Gilead
- AEs of malignancies, excluding non-melanoma skin cancers, utilizing a MST list developed by Gilead
- AEs of non-melanoma skin cancers, utilizing a MST list developed by Gilead
- AEs of gastrointestinal perforation, utilizing a MST list developed by Gilead
- AEs of arterial or venous thrombosis and/or thromboembolism, presented in the following subcategories:
 - AEs of venous thrombosis, utilizing a MST list developed by Gilead
 - AEs of pulmonary embolism, utilizing a MST list developed by Gilead
 - AEs of arterial thrombosis, utilizing the embolic and thrombotic events, arterial Standardised MedDRA Queries (SMQ)
 - AEs of cerebrovascular events, utilizing the ischaemic central nervous system vascular conditions SMQ

For the double-blind phase, the number of subjects with a TE AEI (and SAE), the corresponding PYE, the calculated EAIR, and the exact 95% CIs (defined in Section 8.1.5.3) will be summarized for each treatment group by PT. The EAIR difference (filgotinib – placebo) and corresponding 95% CIs for the difference between treatment groups will also be presented for the double-blind phase of the study.

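### The double-blind adverse event display is said to match the Week 13 semen analysis but has no Week 13 cap, so its crude percentages can compare arms with unequal exposure

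*SAP*

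**What the plan says.** SAP 8.1 defines a double-blind AE display and states: "This analysis will summarize adverse events during the same timeframe as the primary analysis for sperm/semen data". SAP 3.2 gives the same reason for it: "to align with the period summarized for the primary analysis of semen data".

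SAP 6.2 fixes the primary analysis in time: "The primary analysis will be an observed cases analysis at Week 13 while subjects are on double-blind study drug". Table 3-4 in SAP 3.7.2 sets the Week 13 semen window at Days 85 to 112, nominal Day 92. The note under that table reads "Primary analysis includes data up to first dose date of open-label filgotinib (if non-missing) or to last dose date of double-blind drug", with 7 days added after the last dose.

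The AE window in SAP 3.2 and 8.1 ends at one of three points: the day before the first open-label dose, 30 days after the last double-blind dose, or the data cut for subjects still on blinded drug at an interim. The double-blind patient-years rule in SAP 8.1.5.3 has no week limit either. SAP 1.2 says that responders without disease worsening or a sperm decrease "may continue taking study drug in the LTE phase for up to 195 weeks", and SAP 4.2.1 tabulates exposure up to Week 221.

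General AE results are crude. SAP 8.1.6 says "The number and percentage of subjects who experienced at least 1 TEAE will be provided and summarized by SOC, HLT, PT, and treatment", and Grade 3 or higher events are handled the same way. Exposure-adjusted incidence rates (EAIR) are planned in SAP 8.1.7 for adverse events of interest: "For the double-blind phase, the number of subjects with a TE AEI (and SAE), the corresponding PYE, the calculated EAIR".

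**The concern.** Time in this display depends on an outcome that treatment may change. Under the protocol's study design (Section 3), everyone takes blinded drug to Week 13. After that, only responders without a sperm decrease continue blinded drug. Non-responders without a sperm decrease move to open-label filgotinib and leave the display, and subjects with a sperm decrease stop drug. At Week 26 the same kind of selection decides who continues blinded drug in the LTE.

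If one arm has more responders, or keeps them longer, it accumulates more blinded exposure. A crude percentage of subjects with at least one event rises with exposure, so the arms can separate with identical event rates. A reader told that the table covers the Week 13 analysis period would have no reason to suspect this. The SAP contains no AE table limited to Day 1 through Week 13, the only period in which both arms have the same planned follow-up.

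**Working it through.** **Timeline.** The plan's own figure reproduces: 26 + 195 = 221 weeks, and 221 × 7 + 1 = Day 1548, as in SAP 4.2.1. Week 13 is 13 × 7 + 1 = Day 92. The AE window can therefore reach Day 1548 + 30 = Day 1578, about 14 times the Day 112 limit of the primary semen window (1578 / 112 = 14.1).

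**Inputs that are assumptions.** The documents give no AE hazard, LTE uptake or LTE retention. Assumed:
- the same constant AE hazard λ in both arms (0.3 or 1.0 per year);
- non-responders on blinded drug for 15 weeks (0.287 years);
- responders on blinded drug for 26 weeks (0.498 years), after which a share q enters the LTE;
- LTE dropout hazard h = 0.35 per year (1 − exp(−0.35) = 29.5% per year), capped at C = 195 weeks (3.737 years).

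**Formulas.**
- Non-responder with an event: 1 − exp(−λ × 0.287).
- Responder entering the LTE: 1 − exp(−λ × 0.498) × [h/(h+λ) × (1 − exp(−(h+λ)C)) + exp(−(h+λ)C)].
- Responder not entering: 1 − exp(−λ × 0.498).
- Mean LTE time: (1 − exp(−hC))/h = 2.085 years.
- The arm percentage weights these by the response rate and q.

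**Worked case (λ = 0.3, q = 100%).** A non-responder has an event with probability 8.26%. For a responder it is 1 − 0.861 × (0.491 + 0.088) = 50.13%.
- 60% response: 0.6 × 50.13 + 0.4 × 8.26 = 33.4%.
- 40% response: 0.4 × 50.13 + 0.6 × 8.26 = 25.0%.
- Mean exposure: 0.6 × 2.583 + 0.4 × 0.287 = 1.66 years, against 0.4 × 2.583 + 0.6 × 0.287 = 1.21 years.

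| Response by arm | q | Crude %, λ = 0.3 | Crude %, λ = 1.0 | Mean years |
|---|---|---|---|---|
| 60% vs 40% | 100% | 33.4 vs 25.0 | 60.4 vs 48.6 | 1.66 vs 1.21 |
| 60% vs 40% | 70% | 26.9 vs 20.7 | 52.3 vs 43.2 | 1.29 vs 0.96 |
| 60% vs 40% | 0% (no LTE time) | 11.6 vs 10.5 | 33.5 vs 30.7 | 0.41 vs 0.37 |
| 55% vs 50% | 100% | 31.3 vs 29.2 | 57.4 vs 54.5 | 1.55 vs 1.44 |
| 50% vs 50% | any | equal | equal | equal |

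**With a Day 92 cap.** 1 − exp(−λ × 92/365.25) = 7.3% (λ = 0.3) or 22.3% (λ = 1.0), in both arms whatever the response rates.

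**A second set of assumptions.** Protocol 1.3.2 reports 59% versus 41% response in the Phase 2 Crohn's disease study. Using that split, 13 weeks for non-responders, a 30-day tail for responders, 60% to 90% LTE uptake, and LTE stays of 26 to 195 weeks:
- exposure ratio 1.22 to 1.38;
- TEAE gap 7.2 to 11.6 points at 150 events per 100 patient-years;
- Grade 3 or higher gap 1.1 to 5.3 points at 10 per 100 patient-years;
- with no LTE time at all, ratio 1.15 and TEAE gap 4.9 points.

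**Does EAIR alone solve it?** Under a constant hazard, yes: 30.0 versus 30.0 per 100 patient-years at λ = 0.3. If the hazard is 0.6 per year to Week 13 and 0.2 per year afterwards, simulation at 60% versus 40% response and q = 100% gives crude percentages of about 32% versus 26% but EAIR of about 28 versus 31. The direction reverses because the arm with more late time is diluted. A fixed-period table is therefore needed as well.

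**The case against.** **The alignment sentence may be loosely right.** The Table 3-4 note defines primary-analysis data by time on double-blind drug, and SAP 6.2 also reports Week 26 results by double-blind arm. On that reading the two windows have the same structure and differ only in the tail, 7 days against 30, the latter following the TEAE definition. This is a possible reading, but the primary endpoint still uses only the Week 13 window, and exposure remains response-dependent.

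**The display may not be meant to include the LTE.** SAP 1.2 attaches the double-blind phase label to Parts A and B only. The inclusion rules in SAP 3.2, 8.1 and 8.1.5.3 carry no such limit, however, and the disposition categories in SAP 4.1 apply the same label to the blinded LTE. A Week 26 limit would shrink the problem without removing it, because selection starts at Week 13.

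**The size comes mostly from assumed LTE time.** This stands. Without the LTE, the gap at 60% versus 40% falls from 8.4 to 1.1 points (λ = 0.3) and from 11.8 to 2.9 points (λ = 1.0). The model also ignores Part B exits for disease worsening, Week 26 non-response and sperm decreases, except through the lower q. The figures describe the final analysis; interim follow-up would be shorter. The 59% versus 41% split is from Crohn's disease, and SAP 6.7 says few such subjects were enrolled.

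**Some protection exists.** EAIR covers the adverse events of interest and perhaps serious AEs, double-blind exposure is summarised by arm (SAP 4.2.1), and SAP 8.1.8 splits AEs by treatment sequence at the final analysis. None of these adjusts the all-TEAE or Grade 3 or higher tables, and the sequence tables are crude and defined by outcome.

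**The direction may be conservative.** If response is higher on filgotinib, the artefact overstates filgotinib's AE percentages. That is true, but it is still a misleading comparison.

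**Conclusion.** The concern holds. As written, the double-blind AE window is not the primary semen analysis period, and the general TEAE and Grade 3 or higher comparisons are crude percentages over exposure that depends on response. With no true difference, the artefact in the scenarios tabulated runs from zero (equal response and retention), through 1 to 3 points (60% versus 40% response without LTE time, or 55% versus 50% with it), to 8 to 12 points (60% versus 40% with full LTE uptake). These sizes rest on assumed hazards, uptake and retention that the documents do not supply; the mechanism does not. AE displays are descriptive and safety is an exploratory objective, so the consequence is misreading of the safety tables. The change should be made, but it does not threaten the primary endpoint.

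**What to change.** 1. Correct the alignment statement in SAP 8.1 and its counterpart in SAP 3.2. State the actual window, including whether the blinded LTE is in it, and reconcile this with the phase labels in SAP 1.2.
2. Add TEAE, Grade 3 or higher, serious AE and discontinuation tables by randomised arm for a fixed Day 1 to Week 13 period. Count onsets up to the earliest of Day 92, the day before the first open-label dose, or 30 days after the last double-blind dose. Protocol Appendix 2 says "Weeks 13 and 26 must occur after 13 weeks and 26 weeks of drug exposure, respectively", so no planned open-label switch falls before Day 92 and the cap does not depend on response. Drug stopped before about Day 62 (92 − 30) would still shorten follow-up, so show exposure by arm beside the tables. Present these as the randomised AE comparison.
3. For the uncapped double-blind and as-treated displays, preferably extend the EAIR and the MOVER difference of SAP 8.1.5.3 to all TEAEs and Grade 3 or higher TEAEs, noting the constant-hazard assumption. State whether the serious AE reference in SAP 8.1.7 means all serious AEs. This is secondary to item 2.

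The cost is two sentences of SAP text and a few extra outputs using methods already specified. No new data are needed.
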